One biomarker that is being increasingly utilized for the non-invasive monitoring of patients with various malignancies is cell-free DNA (cfDNA). cfDNA consists of short double-stranded DNA fragments shed into the blood by tumor cells undergoing apoptosis or necrosis. We and others have shown that cfDNA can be readily extracted and sequenced from NSCLC patient blood for mutation detection and disease monitoring (Thompson J et al. CCR 2016; Couraud S et al. CCR 2014; Oxnard GR et al. CCR 2014; Newman AM et al. Nature Medicine 2013). While surgically resected tumor or fine needle aspirate have traditionally been the source of tissue for molecular monitoring, these samples often provide insufficient and/or inferior quality DNA for sequencing, and can under-represent the full molecular heterogeneity of the patient's disease, especially in the setting of metastasis. cfDNA thus represents a non-invasive approach for patient monitoring and may allow for a "liquid biopsy" for genomic alterations of the primary or metastatic tumor, monitoring of the disease status, and/or development of resistance to therapy.

In this study, we will collect blood and urine specimens from patients receiving immunotherapy as part of their standard of care for the treatment of NSCLC. We will use various platforms for measurement of new biomarkers, and these biomarkers will be assessed for their ability to predict responsiveness

PROJECT TITLE: A PILOT STUDY TO DEVELOP PREDICTIVE BIOMARKERS FOR THE RESPONSE TO

IMMUNOTHERAPY IN LUNG CANCER

PRINCIPAL INVESTIGATOR/FACULTY SPONSOR: [name], MPH

PROTOCOL SUMMARY VERSION DATE: August, 2018 (VERSION 2)

to immunotherapy, correlation with radiographic response, ability to detect lung cancer specific genetic changes present in the primary tumor (e.g analysis of cfDNA for EGFR mutations), and impact on prognosis (response to therapy, progression free survival and overall survival).

Portions of the blood and urine samples drawn will also be stored for future research.

3- Study Objectives

The overall objective is to develop a comprehensive system to collect blood and urine samples from patients with NSCLC receiving immunotherapy

Primary Outcome Variable

1. Discovery and validation of new blood based biomarkers that predict response to immunotherapy in NSCLC

Secondary Outcome Variable

1. Storage of samples for future research endeavors

4- Location

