The total study duration will be 5 years. Subjects will be considered active participants on days of blood acquisition. Baseline data will be collected by chart review. Cancer outcome data may be collected longitudinally by chart review only until the end of the study.

SUBJECT SELECTION & WITHDRAWAL

6- Inclusion and Exclusion Criteria

A. Inclusion Criteria

1. Advanced Metastatic NSCLC
2. Scheduled to initiate an immune checkpoint inhibitor
3. Age ≥ 18 years
4. Able to provide informed consent

B. Exclusion Criteria

1. Other, unrelated, concomitant active, invasive malignancy

7- Vulnerable Populations

Although vulnerable populations are not specifically excluded from this study, there will be no specific efforts to target these populations.

8- Subject Accrual

Eligible subjects will be identified by physicians, nurse practitioners, and physician assistants at the Abramson Cancer Center and PPMC. A total of 200 patients will be included in this study.

9- Subject Recruitment & Screening

All adult patients being evaluated by the Penn Thoracic Oncology group meeting inclusion/exclusion criteria will be screened for admission into the study. All prospective research subjects will meet with a study team member, the study will be explained, questions answered and the Informed Consent Process will be initiated

10- Data

This study will collect the following specific personal health identifiers (PHI) and other data elements for use at Penn. These data elements will be stored electronically in REDCAP, and will only be accessible to Penn study members. See **section 12** for specific data elements

INVESTIGATIONAL AGENTS

11. Drugs/devices (if applicable)

N/A

STUDY PROCEDURES

12. Procedures

1. Informed consent
2. Collection of baseline clinical information (chart review)
 - a. Baseline demographic data (sex, race, ethnicity)
 - b. Tobacco history
 - c. Medical history
 - d. Performance status
 - e. Baseline tumor related variables, including histology, immunohistochemistry results, TNM stage, sites of tumor involvement
 - f. Results of staging CT scans
 - g. Mutation status as determined by clinical testing of tumor material
 - h. Treatment regimens, including chemotherapy regimen, doses

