3. Blood will be drawn once at baseline prior (up to 50 ml), and the frequency of research blood collection will not exceed the lesser of 50 mL or 3 mL/kg in an 8 week period and will not occur more frequently than 8 times per year. When possible, research blood samples will be drawn at the same time as the clinical sample to minimize discomfort and inconvenience to the patient. The listed time points below are approximations and will depend upon when the patient is having blood drawn for clinical purposes
 1. Baseline – up to 30 ml
 2. 2-4 weeks - up to 20 ml
 3. 8-12 weeks – up to 30 ml
 4. 14-16 weeks – up to 20 ml
 5. 18-24 weeks – up to 30 ml
4. Subjects will be asked if they are willing to provide a single urine specimen in a sterile specimen cup at the time of enrollment
5. Although the vast majority of patients will have had tissue sequencing and immunohistochemical analysis to determine PD-L1 expression, if these analyses have not been performed, we may request that tumor tissue undergo this testing provided sufficient material is available. The result of this information may be disclosed to the patient and primary oncologist.
6. Longitudinal Data collection
 - a. CT imaging to monitor treatment response
 - b. Date of progression, and sites of progression.
 - c. Date of death, if prior to end of study period
7. Analysis of blood and tissue samples. Samples may undergo the following analyses:
 - a. Blood samples will undergo isolation of circulating free DNA and identification of specific mutations using either a PCR or sequencing approach
 - b. Identification of specific proteins or cell surface markers using various protein measurement methods (e.g. mass spectroscopy, flow cytometry)

STATISTICAL PLAN

13. Sample Size Determination

This is a pilot analysis to determine the role of novel biomarkers for use as predictive markers in patients with lung cancer receiving immunotherapy. We are unable to conduct formal sample size analysis given the pilot nature of this study.

14. Statistical Methods

We will use descriptive statistics for variables collected. We will describe the demographic characteristics of subjects using frequencies and percentages for categorical variables and medians and ranges for quantitative variables. Data analysis will focus on the following analyses (based on our primary objective)

1. Prognostic markers: The analysis will determine the association with response rate, PFS, and OS.

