2. When feasible, we will calculate the correlation between markers identified in the blood and in the primary tumor.

SAFETY & ADVERSE EVENTS

15. Potential Risks

The risk of study participation is minimal. The two main risks are loss of confidentiality and the risk of venipuncture. A number of mechanisms are in place to protect subject confidentiality (see above). The risk of venipuncture is minimal. There may be bruising or bleeding, and rarely infection. The overall amount of blood drawn for this study is not to exceed 50 ml not to exceed in an 8 week period and will not occur more frequently than 8 times per year and should not have any clinical implications for study participants.

16. Potential Benefits

Discovery of a minimally invasive biomarker to predict response to immunotherapy has the potential to significantly alter the current management of patients with lung cancer. This study may lead to the development of new methods for the management of patients with lung cancer receiving immunotherapy.

17. Confidentiality & Data Storage

Precautions will be taken to ensure that strict confidentiality is maintained. All source documents will be identified by a unique study ID number (unique for this project). No results will be reported in a personally identifiable manner. Study data will be maintained either on a study-dedicated computer whose files are password protected or in a locked filing cabinet to which only the investigators and their designated staff have access. Data that will be disclosed outside of Penn:

- a. Baseline demographic data (sex, race, ethnicity)
- b. Tobacco history
- c. Performance status
- d. Baseline tumor related variables, including histology, immunohistochemistry results, TNM stage, sites of tumor involvement
- e. Results of staging CT scans
- f. Mutation status as determined by clinical testing of tumor material
- g. Treatment regimens, including chemotherapy regimen, doses

18. Data Safety & Monitoring

PROJECT TITLE: A PILOT STUDY TO DEVELOP PREDICTIVE BIOMARKERS FOR THE RESPONSE TO

IMMUNOTHERAPY IN LUNG CANCER

PRINCIPAL INVESTIGATOR/FACULTY SPONSOR: [name], MPH

PROTOCOL SUMMARY VERSION DATE: August, 2018 (VERSION 2)

Safety data will be monitored by the principal investigator formally on a quarterly basis in the course of study conduct. We plan to have our data reviewed manually by the study coordinator who will bring any discrepancies to the attention of the study team for investigation and resolution.

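### For mutation calls, a correlation reported alone does not show how often blood detects a mutation present in the tumour; Section 14 item 2 should report positive and negative percent agreement

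*Combined protocol and SAP*

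**What the plan says.** Section 2 (Background) lists what the biomarkers will be assessed for. One item is their "ability to detect lung cancer specific genetic changes present in the primary tumor", with EGFR mutations in cell-free DNA as the example.

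Section 12 (Procedures) describes the two measurements to be compared:

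- Tumour: "Mutation status as determined by clinical testing of tumor material". No specimen site is specified.
- Blood: "isolation of circulating free DNA and identification of specific mutations using either a PCR or sequencing approach".

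Section 12 also says that "the vast majority of patients will have had tissue sequencing and immunohistochemical analysis to determine PD-L1 expression". Testing may be requested for the rest if there is enough material. Blood is to be drawn at baseline and at four later approximate time points. Blood work may also include proteins and cell surface markers: "Identification of specific proteins or cell surface markers using various protein measurement methods".

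The analysis is Section 14, item 2. Subject to feasibility, "we will calculate the correlation between markers identified in the blood and in the primary tumor". The section names no coefficient, measurement scale, reference standard or blood sample. It does not mention sensitivity, specificity or percent agreement, and neither does any other section.

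**The concern.** The Background question has a direction: among patients whose tumour carries a mutation, how often does blood find it? The companion question is how often blood is negative when the tissue is negative. Both measurements are essentially yes/no for mutations, so the answer is two proportions from a paired 2x2 table.

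A correlation between two yes/no variables is a single symmetric number. It merges missed mutations, blood-only calls and mutation frequency. A reader given only that number could not tell a blood test that misses half of the tumour mutations from one that misses none but adds calls not seen in tissue. Coefficients for mutations of different frequency would also not be directly comparable.

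**Working it through.** The plan gives no agreement figure, mutation prevalence or expected accuracy, so there is nothing to reproduce. The 200 patients come from Section 8. All prevalence and accuracy values below are assumptions for illustration.

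**Formula.** For two yes/no variables, the Pearson correlation is phi. With prevalence p, sensitivity Se and specificity Sp of blood against tissue, let q = p·Se + (1−p)(1−Sp) be the share of patients who are blood-positive. Then

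phi = (Se + Sp − 1) × √[p(1−p) / (q(1−q))].

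**Step 1. Same phi, same prevalence (p = 0.15), different performance.**

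- Se 46%, Sp 100%: q = 0.069; phi = 0.46 × √(0.1275/0.0642) = 0.65.
- Se 84%, Sp 90%: q = 0.126 + 0.085 = 0.211; phi = 0.74 × √(0.1275/0.1665) = 0.65.

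The first test misses 54% of tumour mutations and the second misses 16%.

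**Step 2. The same point in whole patients (N = 200).**

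- (a) 40 tumour-positive, blood finds 20, no blood-only calls: phi = (20×160 − 20×0)/√(40×160×20×180) = 3200/4800 = 0.667. Sensitivity 50%, specificity 100%.
- (b) 20 tumour-positive, blood finds all 20, plus 20 blood-only calls: phi = (20×160 − 0×20)/√(20×180×40×160) = 3200/4800 = 0.667. Sensitivity 100%, specificity 160/180 = 89%.

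Cohen's kappa does not separate them either. In both tables, observed agreement is 180/200 = 0.90, chance agreement is (40×20 + 160×180)/200² = 0.74, and kappa = 0.16/0.26 = 0.615.

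**Step 3. Same performance, different mutation frequency.**

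- Se 90%, Sp 90%: phi is 0.50 at 5% prevalence and 0.69 at 15%.
- Se 60%, Sp 99%: phi is 0.57 at 2%, 0.66 at 5%, 0.70 at 10%, 0.71 at 15% and 0.69 at 30%.

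The dependence on frequency is clear in the first setting. In the second it is small except for rare mutations. Steps 1 and 2 carry the main argument.

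**Step 4. Precision if proportions are reported (exact Clopper-Pearson 95% intervals).**

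- 15% of 200 = 30 tumour-positive, 18 detected (60%): 41% to 77%.
- 10% of 200 = 20 tumour-positive, 14 detected (70%): 46% to 88%.
- 30% of 200 = 60 tumour-positive, 42 detected (70%): 57% to 81%.
- Only 100 evaluable pairs, 10% positive = 10, 7 detected (70%): 35% to 93%.

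**The case against.** Much can be said for the plan as written.

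- Item 2 names no coefficient, and correlation may be loose wording for concordance. This stands. The documents support saying that the measure is unspecified and, taken as a coefficient alone, does not fit the mutation question. They do not establish that the investigators will report only phi.
- Item 2 covers markers in general. For quantitative markers such as proteins, a correlation is a reasonable description. This stands, and the point is limited to mutation calls.
- Section 14 opens by promising descriptive statistics, which could include counts of blood and tumour calls. This softens the point, but it does not commit to a paired table.
- The detection question is in the Background and not among the Section 3 outcomes. The analysis depends on feasibility and the study is an observational pilot. This stands and limits the importance. However, pilot status excuses the absence of a power calculation; it is not a reason to choose a summary that leaves the stated question open.

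Three stronger readings are tempting, and the documents do not support them.

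- A reader might infer that item 2 contradicts the Background by naming only the primary tumour, because the Background also speaks of "genomic alterations of the primary or metastatic tumor". That phrase describes what cell-free DNA may offer in general. The study's own question in the same section also names the primary tumour, so there is no conflict. What remains is that Section 12 collects mutation status without specifying a site, so the tissue tested may not be the primary.
- A reader might infer that the detection question cannot be answered from this study. It can: both sets of calls are to be collected, and the table can be built.
- A reader might treat every blood-only call as an error. The Background itself says that tissue samples can miss part of the tumour's heterogeneity, so tissue is a comparator and not a perfect truth.

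**Conclusion.** The point holds for mutation calls. The only blood-tumour analysis that Section 14 names would not, as a coefficient reported alone, show how often blood detects a mutation present in the tumour. The ambiguity is large: at 15% prevalence, one phi of 0.65 is compatible with sensitivity of 46% or 84%. These figures rest on assumed prevalence and accuracy. The conclusion does not depend on the particular values, because one coefficient cannot determine two proportions.

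The change is worth making, but its reach is limited. This is a supporting analysis done when feasible, and no data are lost. It does not touch the Section 3 primary outcome, biomarkers that predict response to immunotherapy.

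**What to change.** Reword Section 14 item 2 so that, for mutation calls:

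- the paired 2x2 table is reported for each mutation and for any mutation per patient, with positive and negative percent agreement of the baseline (pre-treatment) blood sample against clinically tested tumour tissue, exact 95% confidence intervals and the number of evaluable pairs;
- a valid blood assay with no mutation detected counts as negative, while failed assays and patients without a tissue result are reported separately as not evaluable;
- blood-only calls are reported as such and not labelled false positives;
- the tissue is the specimen actually tested, with its site and date recorded.

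Keep correlation for quantitative markers such as proteins, as a description of association. It does not show agreement in level: blood values at exactly one tenth of the tumour values still give r = 1.00.

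The cost is a few sentences in Section 14 and two data items (tissue site and date). The visible downside is wide intervals, as in Step 4 of the working. They reflect how few tumour-positive patients there may be for any one mutation, which a single coefficient would not make apparent.
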